18F-AV-1451-A24 Protocol Amendment 1

A Multicenter Screening Study With Flortaucipir F 18 in Patients With Early Symptomatic AD

NCT03467477

Approval date: 17 Apr 2018

Protocol Number: ¹⁸F-AV-1451-A24

A multicenter screening study with flortaucipir F 18 in patients with early symptomatic AD; #2.

Date and Version:

17 April 2018

Amendment #1

Name of Compound:

Flortaucipir F 18 (¹⁸F-AV-1451)

Sponsor:

Avid Radiopharmaceuticals, Inc.

Philadelphia, Pennsylvania USA

CONFIDENTIAL

This material is the property of Avid Radiopharmaceuticals, Inc. (Avid). The information is confidential and is to be used only in connection with matters authorized by Avid and no part of it is to be disclosed to others without prior written permission from Avid.

Sponsor: Avid Radiopharmaceuticals, Inc.	Name of Compound: Flortaucipir F 18 (¹⁸ F-AV-1451)	Active Ingredient(s): 7-(6-[F-18]fluoropyridin-3-yl)-5H-pyrido[4,3-b]indole
Title of Study: ¹⁸ F-AV-1451-A24 A multicenter screening study with flortaucipir F 18 in patients with early symptomatic AD; #2		
Planned number of subjects (Enrolled): Approximately 500		
Name of compound: flortaucipir F 18 (¹⁸ F-AV-1451) Dose: 370 MBq (10 mCi) Route of Administration: Intravenous (IV) bolus		
Study Phase: II		
Study Centers: Approximately 10 centers in North America		
Trial Objectives: The primary objective of the protocol is: 
 To pre-screen patients via a flortaucipir F 18 scan, who have objectively verified cognitive impairment and etiology diagnosed or suspected to be Alzheimer’s disease (AD), and have indicated their interest in participating in Lilly sponsored trials that require tau imaging for inclusion. The secondary objective of the protocol is: 
 To expand the flortaucipir F 18 safety database. 		
Eligibility: See Section 5.3 , Selection of Subjects.		
Study Design: Study ¹⁸ F-AV-1451-A24 is a multicenter screening study in patients with early symptomatic AD (defined as prodromal AD and mild dementia due to AD). All patients will provide informed consent before starting any study procedures. This pre-screening study targets patients who are interested in participating in Lilly AD therapeutic clinical trials and have expressed a preliminary interest in a trial similar to the LMDC trial, and who are not known to meet any of the exclusion criteria for trials similar to LMDC based on medical history and clinical examination. However, consent for this protocol does not constitute consent for any Lilly AD therapeutic trial, and subjects who qualify for this protocol may still		

Sponsor: Avid Radiopharmaceuticals, Inc.	Name of Compound: Flortaucipir F 18 (¹⁸ F-AV-1451)	Active Ingredient(s): 7-(6-[F-18]fluoropyridin-3-yl)-5H-pyrido[4,3-b]indole

fail to qualify for Lilly AD therapeutic trials based on the results of this protocol or based on additional testing performed in those subsequent trials.
		

Screening assessments will include demographic information, cognitive testing, disease history, concomitant medications, vital signs, ECG and medical history. Patients who are deemed eligible to continue will complete a flortaucipir F 18 PET scan.
		

Patients who meet eligibility criteria will participate in this protocol until they have completed their flortaucipir F 18 PET scan and safety follow-up call, or they discontinue, withdraw consent, or if the sponsor decides to end this protocol early.
		

Details of the assessments that will be performed at each visit are detailed in Section 7.1. The following will be completed during the screening visit:
 
 • Informed consent for patient; • Demographics (age, gender, years of education, race, ethnicity); weight/height • Medical and surgical history, concomitant medications; • Vital Signs (pulse, respiratory rate, supine blood pressure); • An ECG will be performed to assess the participant's cardiac status. If an ECG was performed within the last 12 months of the flortaucipir (¹⁸F) PET Imaging Visit and is available for review, the ECG does not need to be repeated. • ApoE status, if available; • Disease history (date/months since symptom onset, date/months since diagnosis, family history of relevant neurologic disease); • Cognitive status interview, including: 
 ○ Mini Mental State Examination (MMSE) to be performed using Serial-7's on all patients; ○ CogState Brief Battery (CBB) to be performed on all patients • A physician will see the patient during the screening visit; and • For women of childbearing potential, a negative serum pregnancy test must be obtained at the screening visit. 
After screening, eligible patients will complete an imaging visit and safety follow-up call, refer to Section 7.1.2 for details
		

Sponsor: Avid Radiopharmaceuticals, Inc.	Name of Compound: Flortaucipir F 18 (¹⁸ F- AV-1451)	Active Ingredient(s): 7-(6-[F-18]fluoropyridin-3-yl)-5H- pyrido[4,3-b]indole
Statistical Methods: Descriptive analyses will be applied to summarize patients' demographic and baseline characteristics, and qualitative and quantitative assessments of the flortaucipir F 18 PET image.		

TABLE OF CONTENTS

1.	INTRODUCTION	10
2.	STUDY OBJECTIVES	12
3.	SPONSOR, INVESTIGATOR(S) AND OTHER PARTICIPANTS	13
4.	TEST DRUG AND CONTROL AGENTS	14
4.1.	Descriptive Name: ¹⁸ F AV-1451	14
4.2.	Radioactive Labeling	14
4.3.	Decay Characteristics	14
4.4.	Packaging flortaucipir F 18 Injection.....	14
4.5.	Storage and Handling flortaucipir F 18 Injection	14
5.	INVESTIGATIONAL PLAN.....	15
5.1.	Overall Design and Plan of the Study.....	15
5.2.	Planned Dosage and Duration of Treatment.....	15
5.2.1.	Flortaucipir F 18 Dosage and Administration	15
5.2.2.	Rationale for Dosages.....	15
5.3	Selection of Subjects.....	15
5.3.1	Inclusion Criteria	15
5.3.3.	Prior and Concomitant Therapy.....	18
5.4	Removal of Subjects from Study.....	19

FDG	¹⁸ F – Fluorodeoxyglucose
GCP	Good Clinical Practice
IB	Investigator's Brochure

ICF	Informed Consent Form
ICH	International Conference on Harmonization
IHC	Immunohistochemistry
IND	Investigational New Drug
Institutional Review Board /Independent Ethics Committee	A board or committee (institutional, regional, or national) composed of medical and nonmedical members whose responsibility is to verify that the safety, welfare and human rights of the subjects participating in a clinical study are protected.
Investigator	A person responsible for the conduct of the clinical trial at a trial site. If a trial is conducted by a team of individuals at a trial site, the investigator is the responsible leader of the team and may be called the principal investigator (PI).
IV	Intravenous
K_a	Dissociation Constant
keV	Kiloelectron volt
LAR	Legally Authorized Representative
MBq	Megabecquerel
mCi	Millicurie
MCI	Mild Cognitive Impairment
MHD	Maximum Human Dose
MMSE	Mini Mental Status Exam
MRI	Magnetic Resonance Imaging
mSv	Millisievert
NDA	New Drug Application
nM	Nanomolar
NOAEL	No Observable Adverse Effect Level

PET	Positron Emission Tomography
PhRMA	Pharmaceutical Research and Manufacturers of America
SAE	Serious Adverse Event
SOP	Standard Operating Procedures

1. INTRODUCTION

Molecular imaging biomarkers have the potential to aid in the diagnosis of patients with cognitive impairment who are being evaluated for Alzheimer's disease (AD) (Dubois, 2010; McKhann, 2011). Positron emission tomography (PET) ligands such as florbetapir F 18 (Wong, 2010) may provide a minimally invasive estimate of cortical beta amyloid (A β) neuritic plaque deposition, a hallmark pathology, and a required element for the evaluation of AD neuropathologic diagnosis (Hyman 2012). Multiple studies comparing amyloid PET scans to histopathologic assessment of amyloid burden, in subjects for whom biopsy samples were available or who came to autopsy after receiving a PET amyloid scan, support the relationship between PET amyloid imaging results and cortical neuritic plaque density (Clark 2011, 2012; Leinonen, 2008; Sojkova, 2011; Kantarci, 2011; Burack, 2010). The largest of these studies (Clark 2012) demonstrated a high sensitivity and specificity for florbetapir PET to discriminate subjects with subsequent autopsy findings of no or sparse neuritic plaques (amyloid negative) from those with moderate to frequent plaques (amyloid positive).

The ability to image brain amyloid with compounds such as florbetapir is an important advance for diagnosis of neurological disease. An amyloid negative florbetapir PET scan indicates the absence of a hallmark pathology and is inconsistent with a diagnosis of AD. However, because amyloid is believed to accumulate very early in the disease process (Jack et al., 2010) and may be present in other diseases or in clinically normal elderly subjects (Sperling et al. 2011; Price and Morris, 1999), the density or distribution of amyloid in subjects with a positive scan is not associated with Alzheimer's disease severity, has not been established to predict rate of future deterioration and has not been established as a tool to predict or monitor response to therapy.

In contrast to A β neuritic plaques, the density and distribution of phosphorylated tau, aggregated in neurofibrillary tangles, increases with AD-related cognitive impairment and correlates with neurodegeneration (Dickson et al., 1997; Duyckaerts et al., 1987). Thus, a PET imaging agent that binds to phosphorylated tau has potential application as a biomarker for disease severity/neurodegeneration and may be useful both for selecting patients for therapy and for monitoring disease progression in therapeutic trials.

Flortaucipir F 18 (¹⁸F-AV-1451) (originally named [F-18]T807 by Siemens Molecular Imaging Biomarker Research group) has been developed as a positron emitting radiopharmaceutical for *in vivo* imaging of tau protein aggregates (Xia et al., 2013). Autoradiography results using tissue sections from human brains showed a strong signal in the grey matter of cortical slices from tau positive brains but weak or no binding in tau negative, A β positive, or tau and A β negative tissue. Scatchard analysis based on this heterogeneous autoradiography assay yielded an estimated K_d of 15nM. A saturation binding experiment using purified Paired Helical Fragment Tau isolated brains of AD patients yielded a K_d value of 0.54 nM.

An updated summary of preclinical and clinical experience pertaining to the safety of flortaucipir (¹⁸F) can be found in the investigator's Brochure. Briefly, preclinical toxicity studies of 19F-AV-1451 (non-radioactive flortaucipir (¹⁸F), "AV-1451") showed a good safety profile with no observable effects at high multiples of the intended maximum

human dose. AV-1451 was positive in the in vitro hERG assay. However, the cardiovascular assessments performed during the dog toxicology studies showed no evidence that AV-1451 prolongs the QT interval at high multiples of relevant clinical doses, and therefore the risk of QT prolongation is not included in the risk profile.

Human dosimetry results for flortaucipir (¹⁸F) showed both hepatobiliary and renal excretion, and total effective dose similar to other approved F-18 radiopharmaceuticals. The organs of the gastrointestinal tract (upper large intestine, small intestine, and liver) received the greatest exposure. The whole body effective dose for a 10 mCi (370 MBq) dose of flortaucipir (¹⁸F) was calculated to be 8.70 mSv. In human clinical studies so far, flortaucipir (¹⁸F) is generally well-tolerated with a low incidence of mild and transient adverse events.

Image assessment showed tracer deposition on brain PET scans to be consistent with that expected for a tracer of aggregated tau protein. Flortaucipir (¹⁸F) initially entered the brain and was subsequently eliminated from the brain in clinically normal and amyloid negative cognitively impaired subjects, yielding only a diffuse pattern of background activity, whereas a regionally distinct gray matter distribution of increased tracer retention was observed in amyloid positive cognitively impaired subjects (Pontecorvo et al., 2017). Preliminary analyses of our Phase II longitudinal study (A05, exploratory cohort) also indicate a relationship between the level and pattern of flortaucipir uptake at baseline, and the rate of decline on cognitive tests over an 18 month period (Mintun, AAIC 2017). These results suggest that it may be possible to use flortaucipir PET scans to enrich clinical studies for subjects with a desired level of AD pathology and a more homogeneous rate of cognitive decline, thus increasing power to detect a treatment effect. Specifically, Lilly and Avid desire to conduct treatment trials at the earliest stage of AD neuropathology to maximize potential patient benefit.

Proposed Lilly AD therapeutic trials intend to target patients with a certain distribution and density of tau neurofibrillary tangles that are hypothesized to be appropriate for certain trials. It is thought that patients with no tau will progress so slowly that a clinical treatment effect could not be discerned, and those with a large tau burden may not be responsive to anti-amyloid or anti-tau therapies as their cognitive impairment is driven primarily by tau pathology. The overarching goal of this protocol is to test this hypothesis by pre-screening patients with flortaucipir F 18 who have been diagnosed with suspected Alzheimer's disease and have indicated their interest to consider participation in Lilly therapeutic clinical trials.

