2. STUDY OBJECTIVES

The primary objective is to pre-screen patients via a flortaucipir F 18 scan, who have objectively verified cognitive impairment and etiology diagnosed or suspected to be Alzheimer's disease, and have indicated their interest in participating in Lilly sponsored trials that require tau imaging for inclusion.

The secondary objective of the study is to expand the flortaucipir F 18 safety database.

[figure not shown]

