5. INVESTIGATIONAL PLAN

5.1. Overall Design and Plan of the Study

Study ¹⁸F-AV-1451-A24 is a multicenter screening study in patients with early symptomatic AD (defined as prodromal AD and mild dementia due to AD).

All patients will provide informed consent before starting any study procedures. This pre-screening study targets patients who are interested in participating in AD therapeutic clinical trials and have expressed a preliminary interest in a trial like the LMDC trial, and who are not known to meet any of the exclusion criteria for trials like LMDC based on medical history and clinical examination. However, consent for this protocol does not constitute consent for the LMDC trial or any other trials, and subjects who qualify for this protocol may still fail to qualify for trials like LMDC or other trials based on the results of this protocol or based on additional testing performed in those subsequent trials.

Screening assessments will include demographic information, cognitive testing, disease history, concomitant medications, vital signs, ECG and medical history. Patients who are deemed eligible to continue will complete a flortaucipir F 18 PET scan.

Patients who meet eligibility criteria will participate in this protocol until they have completed their flortaucipir F 18 PET scan, or they discontinue, withdraw consent, or if the sponsor decides to end this protocol early.

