2 INTRODUCTION

Flortaucipir F 18 (¹⁸F-AV-1451) (originally named [F-18]T807 by Siemens Molecular Imaging Biomarker Research group) is a positron emitting radiopharmaceutical developed for in vivo imaging of tau protein aggregates (Xia et al., 2013). Image assessment showed tracer deposition on brain PET scans to be consistent with that expected for a tracer of aggregated tau protein. Flortaucipir (¹⁸F) initially entered the brain and was subsequently eliminated from the brain in clinically normal and amyloid negative cognitively impaired subjects, yielding only a diffuse pattern of background activity, whereas a regionally distinct gray matter distribution of increased tracer retention was observed in amyloid positive cognitively impaired subjects (Pontecorvo et al., 2017). Preliminary analyses of our Phase II longitudinal study (A05, exploratory cohort) also indicated a relationship between the level and pattern of flortaucipir uptake at baseline, and the rate of decline on cognitive tests over an 18-month period (Mintun, AAIC 2017). These results suggest that it may be possible to use flortaucipir PET scans to enrich clinical studies for subjects with a desired level of AD pathology and a more homogeneous rate of cognitive decline, thus increasing power to detect a treatment effect. Specifically, Lilly and Avid desire to conduct treatment trials at the earliest stage of AD neuropathology to maximize potential patient benefit.

Proposed Lilly AD therapeutic trials intends to target subjects with a certain distribution and density of tau neurofibrillary tangles. It is thought that patients with no tau will progress so slowly that a clinical treatment effect can not be discerned, and those with a large tau burden may not be responsive to anti-amyloid therapy as their cognitive impairment is driven primarily by tau pathology. The overarching goal of AV-1451-A24 is to test this hypothesis by pre-screening subjects with flortaucipir F 18 who have been diagnosed with suspected Alzheimer's disease and have indicated their interest to consider participation in trials such as the Lilly therapeutic clinical trials.

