8.9.1 Qualitative Assessment of Images

The visual read results will be categorized as τ AD+, τ AD++ and τ AD-. The visual read results will be summarized by frequency distribution (count and percentage) for the efficacy population by subject eligibility and overall.

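### Does it matter that both introductions say A24 will test a tau progression-and-response hypothesis, when one scan with no therapy or follow-up cannot test it?

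*Protocol*

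**What the plan says.** The introductions of both documents set out a two-part idea. On progression, the Protocol says "It is thought that patients with no tau will progress so slowly that a clinical treatment effect could not be discerned". On response, it says "those with a large tau burden may not be responsive to anti-amyloid or anti-tau therapies"; the SAP narrows this to "those with a large tau burden may not be responsive to anti-amyloid therapy". Each introduction then states a goal. The Protocol has "The overarching goal of this protocol is to test this hypothesis by pre-screening patients with flortaucipir F 18" and the SAP has "The overarching goal of AV-1451-A24 is to test this hypothesis by pre-screening subjects with flortaucipir F 18". In both, the sentence goes on to describe those patients as people with suspected AD who would consider joining the sponsor's therapeutic trials.

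The formal objectives are different. Protocol section 2 begins "The primary objective is to pre-screen patients via a flortaucipir F 18 scan" and adds one secondary objective, enlarging the tracer's safety database. SAP section 3 gives the same two objectives.

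Under Protocol 5.1, eligible patients take part "until they have completed their flortaucipir F 18 PET scan"; the synopsis adds a safety telephone call. For the imaging result, SAP 8.9.1 plans visual reads "summarized by frequency distribution (count and percentage"), by subject eligibility and overall.

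**The concern.** A hypothesis about rate of progression needs repeated cognitive measurements. A hypothesis about treatment response needs a treatment and an outcome. A24 has neither, yet both documents call testing this hypothesis the study's overarching goal. Neither formal objective mentions it, and no endpoint or analysis is attached to it.

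If the sentence were taken at face value, a study report might present the observed spread of tau reads as evidence for the hypothesis, when the study cannot support or refute it. A related worry is that the quantity A24 can estimate, the share of patients in each visual-read category, is planned without any measure of precision.

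**Working it through.** There is no sample-size calculation to reproduce. SAP 4.5 gives approximately 500 subjects on recruitment grounds, with no error rate, power, effect size or precision target. The check is therefore a comparison of passages, in three steps.

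**1. What a test would need, against what A24 collects**

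- *Progression by tau level* needs at least two cognitive time points. The schedules (Protocol 11.2, SAP 6.1) have MMSE and CBB at screening only. Measurements after screening: 0.
- *Response by tau level* needs a therapy and a response outcome. Protocol 5.2.1 gives a single imaging dose of the tracer. Subjects given a therapy under A24: 0.
- *Follow-up* is one safety call 2 or 3 business days after imaging, and AE reporting ends at 48 hours (Protocol 7.1.2 and 7.7.2).
- *Link to later outcomes*: consent to A24 is not consent to a therapeutic trial (Protocol 5.1), and neither document plans to follow subjects into one.
- *Quantitative tau*: SUVr is computed only for scans read as τAD+ or τAD++ (SAP 6.4.2), so scans read as τAD- have no quantitative value.

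A24 alone therefore cannot test either half.

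**2. Whether anything operative depends on the sentence**

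- Objectives (Protocol 2, SAP 3): pre-screening and the safety database.
- Design discussion (SAP 4.2): pre-screening.
- Sample size (SAP 4.5): recruitment for a pre-screening study.
- General methods (SAP 7.1, 7.8): one group, descriptive statistics, no subgroup analysis.
- Imaging analyses (SAP 8.9.1 to 8.9.3): counts and percentages of reads, SUVr summaries, and a regional listing.
- Safety (SAP 8.10): exposure summary, TEAE tables, and listings.

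None of these refers to progression or response. If the sentence were removed from both introductions, every item would stand unaltered. The same is true of the difference between the two accounts of the hypothesis (anti-amyloid or anti-tau therapies in the Protocol, anti-amyloid therapy alone in the SAP): no analysis uses either version.

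**3. Whether confidence intervals would add anything**

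The approximate 95% half-width for a proportion p among N scans is 1.96 × √(p(1 − p)/N). At p = 0.5:

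- N = 500: 1.96 × √(0.25/500) = 0.0438, or about ±4.4 percentage points.
- N = 350: 1.96 × √(0.25/350) = 0.0524, or about ±5.2 percentage points.

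Both values of N are assumptions. The figure of 500 is approximate enrolment. SAP 8.1.1 defines the enrolled population as everyone who consented and has data in the database, while the imaging analyses use only subjects who were dosed and have a valid scan assessment (SAP 8.1.3). The figure of 350 is illustrative, since neither document gives a valid-scan rate. In either case the planned counts are all that is needed to compute an interval. Printing one would not make the estimate more precise, and no decision in A24 depends on it.

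**The case for a change.** The best argument for a change is that the statement is explicit, current and made in both documents, and that it names this protocol and A24, not the wider development programme. A charitable reading is that the hypothesis is about which tau patterns suit a given trial. That has some support in the Protocol, whose paragraph opens on that idea. It has less in the SAP, which drops the phrase and leaves only the progression and response statements to refer to. One scan would not test trial suitability either. Nor can later trials be assumed to settle the question: the planned therapeutic trials intend to target a certain range of tau, so patients at the extremes may not be followed there. A correction would cost only a few words.

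Most of this stands as a reading of the text: the sentence is inaccurate. What does not stand is the harm. The SAP fixes what is tabulated, and nothing in it leads to a conclusion about progression or response.

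Replacing the goal with estimation of read proportions would bring problems of its own. Estimation is not an objective in either document, so the introduction would still differ from the objectives. Adding that the hypothesis can be examined only in later trials would sit badly with the Protocol's own account of study A05, which related baseline uptake to cognitive decline over 18 months. Describing the A24 scan as the baseline for those trials would assert something neither document says.

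**Conclusion.** The observation is correct: A24 has no therapy, no cognitive measurement after screening and no analysis of progression or response, so it cannot test the hypothesis in its introductions. It is a loose sentence in background text. The objectives, design, sample-size rationale and analyses agree on pre-screening and safety, and following them exactly gives sound descriptive tables. The effect on endpoints, populations, analyses and planned conclusions is nil.

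This rests on the report taking its aims from Protocol section 2 and SAP section 3 and its tables from SAP section 8, as those sections provide. Confidence intervals for the read proportions are a matter of preference and can be derived from the planned output. No change to the plan is called for.
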